8.4 Supportive Care Guidelines

Subjects should receive appropriate supportive care measures as deemed necessary by the treating Investigator. Suggested supportive care measures for the management of adverse events (AEs) with potential immunologic etiology are outlined below. Where

appropriate, these guidelines include the use of oral or intravenous treatment with corticosteroids as well as additional anti-inflammatory agents if symptoms do not improve with administration of corticosteroids.

Note that several courses of steroid tapering may be necessary as symptoms may worsen when the steroid dose is decreased. For each disorder, attempts should be made to rule out other causes such as metastatic disease or bacterial or viral infection, which might require additional supportive care.

It may also become necessary to perform conditional procedures such as bronchoscopy, endoscopy, or skin photography as part of evaluation of the event. Suggested conditional procedures for Events of Clinical Interest (ECI) associated with pembrolizumab, can be found in Appendix I.

The treatment guidelines are intended to be applied when the Investigator(s) determine the events to be related (possible, probable or definite) to trial treatment. Note: if after an evaluation the event is determined not to be related to the trial treatment, the Investigator is instructed to follow the reporting guidance in Appendix A (and Section 15.0). Refer to Section 10.0 for dose modification(s).

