- For **Grade 2-3** total bilirubin or PT/INR, pembrolizumab should be interrupted and steroids given as above. If values don't improve within 12 weeks from date of diagnosis of grade 3 toxicity to baseline or Grade 0-1, pembrolizumab should be permanently discontinued.
- For **Grade 4** total bilirubin or PT/INR, pembrolizumab should be permanently discontinued.

Immune-Mediated Hypophysitis

Hypophysitis occurred in 2 (0.5%) of 411 patients, consisting of one Grade 2 and one Grade 4 case (0.2% each), in patients receiving KEYTRUDA in Trial 1. The time to onset was 1.7 months for the patient with Grade 4 hypophysitis and 1.3 months for the patient with Grade 2 hypophysitis. Both patients were treated with high-dose (greater than or equal to 40 mg prednisone or equivalent per day) corticosteroids followed by a corticosteroid taper and remained on a physiologic replacement dose. Monitor for signs and symptoms of hypophysitis. Administer corticosteroids for Grade 2 or greater hypophysitis. Withhold KEYTRUDA for moderate (Grade 2) hypophysitis, withhold or discontinue KEYTRUDA for severe (Grade 3) hypophysitis, and permanently discontinue KEYTRUDA for lifethreatening (Grade 4) hypophysitis.

Renal Failure and Immune-Mediated Nephritis

Nephritis occurred in 3 (0.7%) patients, consisting of one case of Grade 2 autoimmune nephritis (0.2%) and two cases of interstitial nephritis with renal failure (0.5%), one Grade 3 and one Grade 4. The time to onset of autoimmune nephritis was 11.6 months after the first dose of KEYTRUDA (5 months after the last dose) and lasted 3.2 months; this patient did not have a biopsy. Acute interstitial nephritis was confirmed by renal biopsy in two patients with Grades 3-4 renal failure. All three patients fully recovered renal function with treatment with high-dose corticosteroids (greater than or equal to 40 mg prednisone or equivalent per day) followed by a corticosteroid taper.

Monitor patients for changes in renal function. Administer corticosteroids for Grade 2 or greater nephritis. Withhold KEYTRUDA for moderate (Grade 2) nephritis, and permanently discontinue KEYTRUDA for severe (Grade 3), or life-threatening (Grade 4) nephritis.

Immune-Mediated Hyperthyroidism and Hypothyroidism

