10.0 TREATMENT/ DOSE MODIFICATIONS

10.1 Unacceptable Toxicity

Causality for all adverse events should be assessed and if deemed attributable, attempts should be made toward proper attribution.

Drug-related grade 4 toxicities will require subject to discontinue all study treatment. Intolerable grade 2 and grade 3 toxicities should be managed as per dose modification guidelines listed in the table below. Pembrolizumab therapy may be continued providing the residual adverse events are within permissible ranges for pembrolizumab dosing.

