10.2 Dose Modification Guidelines for Pembrolizumab

Adverse events (AEs) both serious and non-serious associated with pembrolizumab exposure may represent an immunologic etiology. These AEs may occur shortly after the first dose or several months after the last dose of treatment. Pembrolizumab must be withheld for drug-related toxicities and severe or life-threatening AEs as per Table 10 below. See also Section 8.4 for supportive care guidelines and Appendix I.

Dosing interruptions are permitted in the case of medical/surgical events or logistical reasons not related to study therapy (e.g. elective surgery, unrelated medical events, patient vacation, and/or holidays). Subjects should be placed back on study therapy within 3 weeks of the scheduled interruption, unless otherwise discussed with the PI. The reason for the interruption should be documented in the patient's study record.

Table 10.2 Dose Modification and Toxicity Management Guidelines for Immune-related AEs Associated with Pembrolizumab

General instructions:				

 1. Corticosteroid taper should be initiated upon AE improving to Grade 1 or less and continue to taper over at least 4 weeks. 2. For situations where pembrolizumab has been withheld, pembrolizumab can be resumed after AE has been reduced to Grade 1 or 0 and corticosteroid has been tapered. Pembrolizumab should be permanently discontinued if AE does not resolve within 12 weeks of last dose or corticosteroids cannot be reduced to ≤ 10 mg prednisone or equivalent per day within 12 weeks. 3. For severe and life-threatening irAEs, IV corticosteroid should be initiated first followed by oral steroid. Other immunosuppressive treatment should be initiated if irAEs cannot be controlled by corticosteroids. 				
Immune-related AEs	Toxicity grade or conditions (CTCAEv4.0)	Action taken to pembrolizumab	irAE management with corticosteroid and/or other therapies	Monitor and follow-up
Steven-Johnson Syndrome (SJS)	Any	Permanently discontinue	Refer patient for specialized care for assessment and treatment.	If SJS confirmed, permanently discontinue pembrolizumab
Toxic Epidermal Necrolysis (TEN)	Any	Permanently discontinue	Refer patient for specialized care for assessment and treatment.	If TEN confirmed, permanently discontinue pembrolizumab

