Pneumonitis	Grade 2	Withhold	Administer corticosteroids (initial dose of 1-2 mg/kg prednisone or equivalent) followed by taper	Monitor participants for signs and symptoms of pneumonitis Evaluate participants with suspected pneumonitis with radiographic imaging and initiate corticosteroid treatment Add prophylactic antibiotics for opportunistic infections
	Grade 3 or 4, or recurrent Grade 2	Permanently discontinue		
Diarrhea / Colitis	Grade 2 or 3	Withhold	Administer corticosteroids (initial dose of 1-2 mg/kg prednisone or equivalent) followed by taper	
 • Monitor participants for signs and symptoms of enterocolitis (ie, diarrhea, abdominal pain, blood or mucus in stool with or without fever) and of bowel perforation (ie, peritoneal signs and ileus). • Participants with \geq Grade 2 diarrhea suspecting colitis should consider GI consultation and performing endoscopy to rule out colitis. • Participants with diarrhea/colitis should be advised to drink liberal quantities of clear fluids. If sufficient oral fluid intake is not feasible, fluid and electrolytes should be substituted via IV

	Grade 4	Permanently discontinue		infusion.
AST / ALT elevation	3	Withhold	Administer corticosteroids (initial dose of 0.5- 1 mg/kg prednisone or equivalent) followed by taper	Monitor with liver function tests (consider weekly or more frequently until liver enzyme value returned to baseline or is stable
	4	Permanently discontinue --see exception below ²	Administer corticosteroids (initial dose of 1-2 mg/kg prednisone or equivalent) followed by taper	
Increased bilirubin	Grade 2	Withhold	Administer corticosteroids (initial dose of 0.5- 1 mg/kg prednisone or equivalent) followed by taper	Monitor with liver function tests (consider weekly or more frequently until liver enzyme value returned to baseline or is stable
	Grade 3 or 4	Permanently discontinue	Administer corticosteroids (initial dose of 1-2 mg/kg prednisone or equivalent) followed by taper	
Type 1 diabetes mellitus (T1DM) or Hyperglycemia	Newly onset T1DM or Grade 3 or 4 hyperglycemia associated with evidence of β -cell failure	Withhold	Initiate insulin replacement therapy for participants with T1DM Administer anti-hyperglycemic in participants with hyperglycemia	Monitor participants for hyperglycemia or other signs and symptoms of diabetes.

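### For Grade 3 total bilirubin, Section 9.1.4 interrupts pembrolizumab and by implication permits re-dosing, while Table 10.2 stops it permanently

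*Combined protocol and SAP*

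**What the plan says.** **Section 9.1.4, immune-mediated hepatitis.** The closing bullets deal with total bilirubin and PT/INR together. For Grade 2-3, "total bilirubin or PT/INR, pembrolizumab should be interrupted and steroids given as above". If values do not "improve within 12 weeks from date of diagnosis of grade 3 toxicity to baseline or Grade 0-1, pembrolizumab should be permanently discontinued". The last bullet makes the stop immediate when either test reaches Grade 4. Earlier in the same subsection, treatment is also to be interrupted when raised transaminases or alkaline phosphatase come with Grade 3 total bilirubin.

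**Table 10.2.** The row "Increased bilirubin" has two lines: withhold at Grade 2, and permanently discontinue at Grade 3 or 4. General instruction 2 covers patients whose drug has been withheld: "pembrolizumab can be resumed after AE has been reduced to Grade 1 or 0 and corticosteroid has been tapered".

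**Where dosing decisions are sent.** Section 8.4 refers the reader to Section 10.0 for dose modification. Section 10.1 says "Intolerable grade 2 and grade 3 toxicities should be managed as per dose modification guidelines listed in the table below". Section 10.2 says "Pembrolizumab must be withheld for drug-related toxicities and severe or life-threatening AEs as per Table 10 below".

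**Appendix I, hepatic.** The last bullet holds drug when AST or ALT and total bilirubin pass stated multiples of the upper limit of normal while alkaline phosphatase stays below its own limit. Monitoring then continues until values are at baseline or below Grade 3.

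**The concern.** Both rules are current text and both apply to a treatment-related rise in bilirubin. At Grade 3 they lead to different treatment: a hold with a recovery window, or the end of study drug. A physician working from Section 9.1.4, whose title is the management of agent-specific adverse events, could restart pembrolizumab in a patient whom Table 10.2 has permanently stopped. This is a hepatocellular carcinoma trial that admits Child-Pugh scores up to 7, so a liver dosing rule should have one reading.

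The consequence for analysis is small. Section 16.5 summarises the number of doses and the reasons for discontinuation descriptively, and those summaries would partly reflect which section was followed.

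**Working it through.** No figure in the plan needs reproducing; the check is a comparison of texts.

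**Step 1. Action by grade of total bilirubin.**

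| Grade | Section 9.1.4 bullets | Table 10.2 | Same immediate action? |
|---|---|---|---|
| 2 | Interrupt, give steroids | Withhold, give steroids | Yes |
| 3 | Interrupt, give steroids; permanent stop only if not back to baseline or Grade 0-1 within 12 weeks of the Grade 3 diagnosis | Permanent stop | No |
| 4 | Permanent stop | Permanent stop | Yes |

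The conflict is confined to Grade 3.

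**Step 2. Is there an exemption that removes it?** Footnote 2 is the table's only liver exception, and it concerns AST and ALT. Section 10.2.1 contains no carve-out for Grade 3 bilirubin. General instruction 2 permits resumption where drug has been withheld; it does not reach a patient whom the table has permanently discontinued.

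**Step 3. Does Section 9.1.4 permit re-dosing?** By implication, yes. It uses the language of interruption, and it makes the permanent stop depend on failure to recover. A patient who recovers in time has met no stopping condition in that section. There is no sentence specific to bilirubin that says to resume. The nearest restart sentence is the general one under other immune-mediated adverse reactions, which allows restart while the reaction stays at Grade 1 or less.

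**Step 4. Is it one stray sentence?** No. The earlier sentence in Section 9.1.4 also interrupts for Grade 3 bilirubin when transaminases or alkaline phosphatase are raised. The Appendix I bullet sets no upper bilirubin limit and follows values until below Grade 3, so it too can be read as a hold at Grade 3.

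**Step 5. Which text governs?** Sections 8.4, 10.1 and 10.2 all point to Section 10, so the table is the likelier rule. They are cross-references. None says that the table displaces Section 9.1.4.

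**Step 6. Size of the difference for one patient.** 12 weeks x 7 days = 84 days; 84 / 21 = 4 cycles. After a Grade 3 event, Section 9.1.4 allows up to 84 days from diagnosis for recovery; Table 10.2 allows 0.

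**The case against.** The strongest reply is that the protocol already settles the matter. Three sections direct dosing decisions to Section 10, and Section 9.1.4 belongs to a chapter on drug formulation and procurement. Harm requires a physician to follow 9.1.4 and pass over those pointers. This lowers the likelihood of an error but does not remove the contradiction: the 9.1.4 bullets are graded dosing instructions still in force, and if the table governs, they are wrong as they stand.

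A second reply is that hold-and-recover may be intended. The revision history records an FDA-recommended bilirubin criterion based on non-resolution, and a later change of hepatic resolution to 12 weeks. Version 5.0 then updated the dose modification table. These entries describe past changes and are not themselves evidence of error. That Section 9.1.4 was simply not realigned afterwards is an inference. Whether Grade 3 bilirubin should end treatment in this disease is a clinical decision, so the sponsor should confirm the table's rule when making the edit.

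A reader might also infer more than the documents support:

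- **That Grade 2 events have no time limit in Section 9.1.4.** The bullets start their 12 weeks at Grade 3, but the same section has a general provision for immune-related events: discontinuation is to be considered if they have not improved within 12 weeks of the start of Grade 2 toxicity. It is discretionary, but it exists. Footnote 3 of the table does not help this reading, since it is attached to the row for all other immune-related events.
- **That many patients would be affected.** No rate of drug-related Grade 3 bilirubin is given. The nivolumab study in Section 1.1 names AST, ALT and lipase as its Grade 3-4 events above 5%, not bilirubin. Any expected count would rest on an assumed rate.
- **That Table 10.2 should override Section 9.1.4 throughout.** Section 9.1.4 requires a permanent stop for Grade 4 hypophysitis and Grade 4 hyperthyroidism, where the table allows either withholding or stopping. General precedence would loosen those stops and conflict with Section 10.1, which ends treatment for drug-related Grade 4 toxicity.

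**Conclusion.** The inconsistency is real and narrow. For treatment-related Grade 3 total bilirubin, Section 9.1.4 prescribes interruption with up to 12 weeks to recover, and Table 10.2 prescribes a permanent stop. Grades 2 and 4 agree on the immediate action. Confidence in the conflict is high because it rests on current text with no exemption. Two parts are interpretation: that 9.1.4 permits re-dosing, which follows from its conditional stop and is not stated for bilirubin; and that the table is meant to govern, which the cross-references support but no sentence declares.

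This should be corrected because it is a patient-level safety instruction and the correction is cheap. It is not a flaw in the design: the Simon boundaries, the sample size and the primary endpoint analysis do not depend on it.

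**What to change.** Subject to the sponsor's confirmation that the table states the intended rule:

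1. In the Section 9.1.4 bullets, separate total bilirubin from PT/INR. For bilirubin, state: at Grade 2, withhold, then resume or stop under general instruction 2 of Table 10.2; at Grade 3 or 4, discontinue permanently.
2. Leave the PT/INR rule as it is. Table 10.2 has no PT/INR row, so deleting the bullets would remove the only specific rule for it.
3. In the earlier 9.1.4 sentence on Grade 3 bilirubin with raised transaminases or alkaline phosphatase, and in the Appendix I hepatic hold bullet, add that Grade 3 or 4 bilirubin means permanent discontinuation under Table 10.2.
4. Add one precedence sentence limited to increased bilirubin: Table 10.2 governs over Section 9.1.4 and Appendix I for that event. Keep it to bilirubin so that the mandatory Grade 4 stops in 9.1.4 and 10.1 are untouched.

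The cost is an amendment to wording, with no new visits, data or analyses. The clinical downside is that a patient with Grade 3 bilirubin who recovers, and who could have restarted under Section 9.1.4, loses study drug.

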Colitis (including microscopic colitis) occurred in 4 (1%) of 411 patients, including Grade 2 or 3 cases in 1 (0.2%) and 2 (0.5%) patients, respectively, receiving KEYTRUDA in Trial 1. The median time to onset of colitis was 6.5 months (range 2.3-9.8). The median duration was 2.6 months (range 0.6 weeks-3.6 months). All three patients with Grade 2 or 3 colitis were treated with high-dose corticosteroids (greater than or equal to 40 mg prednisone or equivalent per day) with a median initial dose of 70 mg/day of prednisone or equivalent; the median duration of initial treatment was 7 days (range 4-41), followed by a corticosteroid taper. One patient (0.2%) required permanent discontinuation of KEYTRUDA due to colitis. All four patients with colitis experienced complete resolution of the event. Monitor patients for signs and symptoms of colitis. Administer corticosteroids for Grade 2 or greater colitis. Withhold KEYTRUDA for moderate (Grade 2) or severe (Grade 3) colitis, and permanently discontinue KEYTRUDA for life-threatening (Grade 4) colitis.

Immune-Mediated Hepatitis

Hepatitis (including autoimmune hepatitis) occurred in 2 (0.5%) of 411 patients, including a Grade 4 case in 1 (0.2%) patient, receiving KEYTRUDA in Trial 1. The time to onset was 22 days for the case of Grade 4 hepatitis which lasted 1.1 months. The patient with Grade 4 hepatitis permanently discontinued KEYTRUDA and was treated with high-dose (greater than or equal to 40 mg prednisone or equivalent per day) systemic corticosteroids followed by a corticosteroid taper. Both patients with hepatitis experienced complete resolution of the event.

Elevated transaminases and alkaline phosphatase may be seen during treatment. Treatment should be interrupted when transaminase or alkaline phosphatase increases are accompanied by Grade 3 total bilirubin, and/or Grade 3 coagulation tests (e.g., International Normalized Ratio [INR]), or if subjects are clinically symptomatic.

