- For **Grade 2 events**, treat with corticosteroids. When symptoms improve to Grade 1 or less, steroid taper should be started and continued over no less than 4 weeks.

Replacement of appropriate hormones may be required as the steroid dose is tapered.

- For **Grade 3-4** events, treat with an initial dose of IV corticosteroids followed by oral corticosteroids. When symptoms improve to Grade 1 or less, steroid taper should be started and continued over no less than 4 weeks. Replacement of appropriate hormones may be required as the steroid dose is tapered.
- **Hyperthyroidism or Hypothyroidism:**

Thyroid disorders can occur at any time during treatment. Monitor patients for changes in thyroid function (at the start of treatment, periodically during treatment, and as indicated based on clinical evaluation) and for clinical signs and symptoms of thyroid disorders.

 - **Grade 2** hyperthyroidism events (and **Grade 2-4** hypothyroidism):
 - In hyperthyroidism, non-selective beta-blockers (e.g. propranolol) are suggested as initial therapy.
 - In hypothyroidism, thyroid hormone replacement therapy, with levothyroxine or liothyronine, is indicated per standard of care.
 - **Grade 3-4** hyperthyroidism
 - Treat with an initial dose of IV corticosteroid followed by oral corticosteroids. When symptoms improve to Grade 1 or less, steroid taper should be started and continued over no less than 4 weeks. Replacement of appropriate hormones may be required as the steroid dose is tapered.
- **Hepatic:**
 - For **Grade 3** events, monitor liver function tests more frequently until returned to baseline values (consider weekly).
 - Treat with IV or oral corticosteroids
 - For **Grade 4** events, treat with intravenous corticosteroids for 24 to 48 hours (or longer if clinically indicated). Monitor LFTs labs at least weekly until Grade 0-1 or baseline at Investigator discretion.
 - When symptoms improve to Grade 2 or less, a steroid taper should be started and continued over no less than 4 weeks.
 - Hold drug if an elevated AST or ALT lab value that is $\geq 5X$ the upper limit of normal (ULN) **and** an elevated total bilirubin lab value that is $\geq 2X$ the ULN **and**, at the same time, an alkaline phosphatase lab value that is $< 2X$ the ULN, as determined by way of protocol-specified laboratory testing or unscheduled laboratory testing.* Monitor labs tests more frequently until AST, ALT and total bilirubin values return to baseline or $<$ grade 3.

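### Two stop rules conflict: Section 9.1.4 and Table 10.2 disagree on grade 3 bilirubin, and Section 10.1 and Table 10.2 disagree on grade 4 endocrine events

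*Combined protocol and SAP*

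**What the plan says.** **Grade 3 bilirubin.** Under Immune-Mediated Hepatitis, Section 9.1.4 treats grade 2-3 total bilirubin or PT/INR by interrupting pembrolizumab and giving steroids. A permanent stop follows if values do not "improve within 12 weeks from date of diagnosis of grade 3 toxicity to baseline or Grade 0-1, pembrolizumab should be permanently discontinued". Grade 4 is a separate item with immediate permanent discontinuation. The same subsection also says: "Treatment should be interrupted when transaminase or alkaline phosphatase increases are accompanied by Grade 3 total bilirubin". The increased-bilirubin row of Table 10.2 withholds drug at grade 2 and then reads: "Grade 3 or 4 Permanently discontinue Administer corticosteroids (initial dose of 1-2 mg/kg prednisone or equivalent) followed by taper".

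**Grade 4 endocrine events.** Section 10.1 takes patients off all study treatment for drug-related grade 4 toxicity, with no endocrine exception. It sends only lower grades to the table: "Intolerable grade 2 and grade 3 toxicities should be managed as per dose modification guidelines listed in the table below". Table 10.2 nevertheless covers grade 4 endocrine events. Drug continues through grade 2-4 hypothyroidism. It is withheld for new type 1 diabetes or for grade 3-4 hyperglycemia with beta-cell failure. For grade 3-4 hypophysitis and hyperthyroidism, withholding or stopping is left to the physician. The note under the table allows drug to resume after a withheld grade 3-4 endocrinopathy once it is grade 2 or lower and controlled. Section 9.1.4 requires a permanent stop for grade 4 hypophysitis and grade 4 hyperthyroidism, and allows isolated hypothyroidism to be treated without interruption.

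**Cross-references.** Section 8.4 says "Refer to Section 10.0 for dose modification(s", and Section 10.2 says "Pembrolizumab must be withheld for drug-related toxicities and severe or life-threatening AEs as per Table 10 below".

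**The concern.** Whether a patient may receive pembrolizumab again after a severe hepatic or endocrine toxicity is an individual safety decision. Here the answer depends on which section the treating physician reads. All patients have HCC, and Child-Pugh scores up to 7 are eligible, so liver function is a sensitive area.

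Study-level monitoring may not catch a divergence. The toxicity guideline in Section 17.2.2 leaves out reversible elevation of liver function tests. If bilirubin counts as such a test (the section does not say), a recovered grade 3 rise would not count toward stopping the study. The patient-level rule would then be the main protection.

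**Working it through.** No figure in the plan needs reproducing. The check sets the current rules side by side.

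| Event (drug-related) | 9.1.4 | 10.1 | Table 10.2 | Can one action meet all? |
|---|---|---|---|---|
| Grade 3 bilirubin, no recovery in 12 weeks | Interrupt, then permanent stop | Refers to table | Permanent stop | Yes, stop |
| Grade 3 bilirubin, recovers in 12 weeks | Interrupt; no stop required | Refers to table | Permanent stop | Restart breaks the table; stopping goes beyond 9.1.4 |
| Grade 4 hypothyroidism | Isolated cases: no interruption | Stop | Continue | No |
| Grade 4 hyperglycemia with beta-cell failure | No event-specific rule | Stop | Withhold, may resume | No: 10.1 ends treatment, the table only withholds |
| Grade 4 hypophysitis | Permanent stop | Stop | Withhold or stop, at discretion | Yes, always stop |
| Grade 4 hyperthyroidism | Permanent stop | Stop | Withhold or stop, at discretion | Yes, always stop |

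**Bilirubin.** Both rules stop drug at once, so the difference arises only after recovery. Section 9.1.4 implies restart then but does not state it. Because it lists grade 4 separately for immediate discontinuation, its softer handling of grade 3 looks deliberate.

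**Endocrine.** The first two endocrine rows are true contradictions. In the last two, the table makes optional a stop that 10.1 and 9.1.4 make mandatory.

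**How many patients.** The documents give no bilirubin rate for pembrolizumab in HCC. Section 1.1 describes a nivolumab HCC trial of 41 patients and lists grade 3-4 events above 5%; bilirubin is not among them. If the rate here were 0 to 5% (an assumption, from a different drug), the expected number is 28 × 0 = 0 to 28 × 0.05 = 1.4 of 28 patients. With only 41 patients behind it, the true rate could be higher. The range also counts grade 4 events and patients who do not recover, for whom the two rules agree, so the affected group is a subset.

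For endocrine events, Section 9.1.4 reports 34 cases of hypothyroidism among 411 melanoma patients, one of them grade 3, and mentions none at grade 4. It gives no count for diabetes or hyperglycemia in those 411. It reports one grade 4 hypophysitis. At 1/411, 28 patients would yield 28 × 1/411 = 0.07 events, and the chance of at least one is 1 − (410/411)^28 = 6.6%. That figure concerns an event for which the texts can be reconciled, so it does not measure the two true contradictions.

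**The case against.** The best defense is that the operative rule is fairly clear. Sections 8.4, 10.1 and 10.2 all direct dose modification to Section 10 or its table, and the revision history records that amendment 5.0 was made to update that table. Section 9.1.4 also provides for the sponsor and treating investigator to discuss permanent discontinuation for an immune-related event, which makes an unreviewed re-exposure less likely.

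Much of this stands for bilirubin: the table is the likelier rule and the stricter one. It does not remove the conflict. No section gives the table precedence, and 9.1.4 is more than background, since its hepatitis text carries trial instructions such as the viral-load limit and three-weekly viral testing. For grade 4 endocrine events, pointing to Section 10 settles nothing, because both rules sit there. The introduction to 10.2 claims life-threatening events for the table, while 10.1 releases only lower grades to it.

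A reader might infer more than the documents support:

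- *All four endocrine rows are irreconcilable.* Always stopping satisfies every section for hypophysitis and hyperthyroidism.
- *Appendix I is a third, competing stop rule.* Section 10.2 does say "See also Section 8.4 for supportive care guidelines and Appendix I", and the appendix holds drug for combined transaminase and bilirubin elevation, with monitoring "until AST, ALT and total bilirubin values return to baseline or" below grade 3. But it describes suggested supportive care and a threshold for further evaluation, and it authorizes no restart.
- *The marker for footnote 2 is simply on the wrong AST/ALT row.* It sits at grade 4 while the footnote describes grade 3. Yet an exception makes sense only beside a permanent stop, and the grade 3 row already says to withhold. The intended place is unclear.

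**Conclusion.** The conflicts are real in the current text and cannot all be followed as written. They are minor. For grade 3 bilirubin the disagreement is confined to patients who recover, after a rule that stops drug immediately in either case. For grade 4 hypothyroidism and grade 4 hyperglycemia with beta-cell failure, 10.1 and the table require different actions. For grade 4 hypophysitis and hyperthyroidism the conflict is mandatory against optional stopping.

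Events are expected to be rare. That expectation rests on nivolumab data in 41 HCC patients and pembrolizumab data in 411 melanoma patients, neither of which is this drug in this population. A reader might also infer a statistical consequence; none is shown. The two-stage design, its power and the disease control rate do not depend on which rule applies.

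**What to change.** Make one wording amendment, confirmed by the clinical lead:

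1. State in Section 10 that Table 10.2 governs dose modification for immune-related adverse events.
2. In the 9.1.4 bilirubin item, make immune-related grade 3 bilirubin follow the table (permanent discontinuation). Keep the existing interrupt-and-recover rule for PT/INR, which has no row in the table, and for bilirubin rises with another established cause. A blanket change would sweep in rises from biliary obstruction or tumor progression, which 9.1.4 itself lists among the causes to work up.
3. Add to 10.1 an exception for endocrinopathies managed under Table 10.2, and align the 9.1.4 wording on grade 4 hypophysitis and hyperthyroidism with it.
4. Have the clinical lead confirm which AST/ALT row footnote 2 belongs to before anything is moved.

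There is no sample-size or analysis cost. The clinical costs are two. Patients who recover from immune-related grade 3 bilirubin could not restart. The endocrine exception relaxes the mandatory stop in 10.1 and, for grade 4 hypophysitis and hyperthyroidism, in 9.1.4. The clinical lead has to accept both.
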